**Please save frequently**

- c) **Describe the study design (e.g., single/double blind, parallel, crossover, control, experimental, observational, etc.). If the study is investigator-initiated, a timeline for individual subject recruitment, follow-up, and analysis for the study is required. Also, indicate if the subjects will be randomized.**

Single blind (Subject) randomized, active control study. Subjects will be randomized 1:1 using the rand function in Microsoft Excel program.

Timeline: There will be a 2 year recruitment period during which patients will be recruited and eligible to participate. Eligible patients are those with chronic inflammatory sinonasal disease for whom frontal drill out procedure is indicated after evaluation by otolaryngologist. Patients eligible for the study and consenting to participate will be randomly assigned to one of two treatment groups: 1) Nasopore group will receive frontal drill out procedure as indicated with Kenalog-soaked Nasopore stent applied to the post-operative outflow tract and 2) Propel stent group will receive frontal drill out procedure as indicated followed by Propel stent placement applied to the post-operative outflow tract.

After the surgery, we will ask patients to follow up 5 times: post-operatively once between week 1-2, once between week 6-8, month 6, month 12, and month 24. All visits are standard of care.

During those visits, patients will fill out a short research related questionnaire that will ask about whether or not their symptoms have improved after surgery. We will also assess sinus cavities with rigid nasal endoscopy. Surgical complications will be documented and SNOT-22 scores will be determined by patients filling out SNOT-22 questionnaire at each visit.

Preliminary analysis will be performed once 5 patients have been enrolled and then every 6 months thereafter until 2 years of follow up of the last subject. We expect enrollment to occur over a period of 2 years.

- d) **If subjects will be given placebo, please justify placebo use. \*?HELP?\***

N/A

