## 1. Background

Page numbers from a sponsor's protocol/grant may be referenced in 1a and 1b.

- a) **Provide an introduction and background information. Describe past experimental and/or clinical findings leading to the formulation of the study, if applicable. Investigator Initiated studies must cite references in the response provided or attach a bibliography. \*?HELP?\***

Endoscopic sinus surgery is commonly used to manage chronic inflammatory frontal sinus disease that is not adequately controlled with medical therapy alone. In recalcitrant cases, a more extensive procedure called the modified endoscopic Lothrop procedure or frontal drill-out (FDO) procedure is often performed [1, 2]. The frontal drill-out procedure is performed endoscopically and its goal is to create one large common cavity between the left and right frontal sinuses and nasal cavities to allow adequate drainage and communication for subsequent drug delivery through sinonasal irrigations if indicated.[3, 4] Failure of this procedure is most commonly the results of re-stenosis of the outflow tract due to scarring, adhesions, or progressive disease such as polyposis.[5, 6] One meta analysis assessing the long-term complications of frontal drillouts reported an overall failure rate to be 13.9%, defined as those individuals needing further surgery.[2] Another clinical trial reported a failure rate for a 200-person study to be 30%.[7]

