**Please save frequently**

Page numbers from a sponsor's protocol/grant may be referenced in 3b, 3c, and 3d.

- b) **Describe all the procedures, from screening through end-of-study, that the human subject must undergo in the research project, including study visits, drug treatments, randomization and the procedures that are part of standard of care. Specify which procedures are for research and which are standard of care. Please note: The box below is for text only. If you would like to add tables, charts, etc., attach those files in the Attachment section (#16).**

Patients who present with chronic inflammatory frontal sinus pathology with indication for frontal sinus surgery will be evaluated for frontal drill out candidacy per physician judgment and consented. Once consented, the patients will be randomized 1:1 using the "rand" function (random number generator) in Microsoft Excel program. Nasopore group will receive frontal drill out procedure as indicated with Kenalog-soaked Nasopore while the Propel stent group will receive the Propel Stent after frontal drillout. Lund-McKay CT staging system, a part of the standard of care, to determine overall and frontal sinus score will be used to help stage and evaluate patients pre-operatively. A preoperative SNOT-22 score, also done as standard of care, will be obtained to assess symptom burden. Those who undergo the procedure and have consented to participate in the study will be asked to present to the otolaryngology clinic for regularly scheduled follow-up as part of standard of care, where symptoms and complications will be assessed. Rigid nasal endoscopy and SNOT-22 score are standard of care for routine follow-up of patients with chronic inflammatory sinonasal disease and will be performed at each of the 5 visits: post-operatively 1-2 weeks, 6-8 weeks, month 6, month 12, and month 24. This data will be abstracted from the records for research purposes. The data collected from the medical record includes the patient's current ENT-related active medical problems.

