- d) **Describe how data analysis will be performed (statistical tests, methods of evaluating data) and indicate the smallest group/unit for which separate reporting will occur. For studies involving a questionnaire, if data and reliability information are available, please describe or provide references. For full board, unfunded studies describe sample size determination and power analysis. If none, please justify.**

The SNOT-22 score assesses symptomatic improvement and burden for patients with rhinosinusitis and is a clinically validated measure with high internal validity, correlation to its impact on quality of life, and longitudinal stability after sinus surgery. The minimal clinically important difference (MCID) for SNOT-22 is 9 points. [1, 2, 3, 4,5] From historical SLU otolaryngology practice data, patients who present to the otolaryngology clinic undergoing sinonasal surgery have a mean SNOT-22 score of  $42.0 \pm 8.0$ .

For this randomized, active control study of two types of sinonasal stents with steroid, we are interested in determining whether the cheaper and more available alternative (Nasopore and Kenalog) is similar to an accepted treatment (Propel stent) in symptom control at 24 months as measured by post-operative SNOT-22 scores.

For our sample size determination, we explore the lower limit of a 95% confidence interval (CI) around the mean difference between post-operative SNOT-22 scores of the two groups. We'll define the lower limit of the CI, or the margin of inferiority, as -8, which does not include the predetermined MCID of -9.  
We set power = 0.8 and alpha = 0.05.

Given: # subjects in each group =  $n = [(2(SD)^2) * (z_{1-(\alpha/2)} + z_{1-B})^2] / [(u_1 - u_2)^2]$  [ref 6]  
SD = 8.0, from SLU historical data  
 $[(z_{1-(\alpha/2)} + z_{1-B})]^2 = 7.8$ , estimated from z-tables,  $\alpha = 0.05$  and  $B = 0.2$

IF  $u_1 - u_2 = -8$  then  $n = 16$  subjects

To be conservative in our sample size calculation, we'll use  $u_1 - u_2 = -5$ , which yields a sample size of 40.

If we assume attrition rate of 10%, we estimate we'll need 45 subjects per group and a total of 90 subjects.

Difference in rates of complications will also be determined by chi-square testing for equality of proportions between groups. As these outcomes are expected to be few, our target sample size may not be adequate to determine statistical significance of differences. Reporting these complication rates nonetheless informs clinical practice.

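### Excel RAND allocation, read naturally, is simple randomisation, and polyposis, which the plan names as a cause of failure, is handled in neither the allocation nor the SNOT-22 analysis

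*Combined protocol and SAP*

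**What the plan says.** Section 2c (study design) gives the method in one sentence: "Subjects will be randomized 1:1 using the rand function in Microsoft Excel program". Section 3b puts it in sequence, "Once consented, the patients will be randomized 1:1 using the" Excel function, which it describes as a random number generator. Neither section mentions blocks, strata, minimisation, a list prepared in advance, or how an assignment is stored or concealed.

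Section 3d plans fixed arm sizes: "we estimate we'll need 45 subjects per group and a total of 90 subjects", built from 40 evaluable per group and 10% attrition. Section 8b sets accrual at 90 and requires prior IRB approval to exceed it, so a short arm cannot simply be topped up. For SNOT-22, section 3d says "we explore the lower limit of a 95% confidence interval (CI) around the mean difference" and names no baseline covariate.

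Section 1a lists "progressive disease such as polyposis" beside scarring and adhesions as reasons why the opening re-stenoses and the procedure fails. Aim 3 in section 2b looks at complications by frontal sinus pathology, so pathology has to be recorded in any case.

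**The concern.** Drawing each patient's arm independently after consent does not deliver the 45 per group that section 3d assumes. It also leaves the polyp share of each arm to chance, in a single-site trial of 90. If polyp status affects month-24 symptoms, that chance variation widens the confidence interval for the treatment difference, and the stated analysis does nothing to remove it. At stake are some avoidable imprecision in the main comparison, and a published baseline table that could show a visible imbalance with no pre-specified way of dealing with it.

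**Working it through.** **Inputs.** From section 3d: SD ("SD = 8.0, from SLU historical data"), difference 5, 40 evaluable and 45 enrolled per group, 10% attrition, and "We set power = 0.8 and alpha = 0.05", with the two-sided z value in the formula. Not in the documents, so assumed: polyp prevalence 20-60%, and a shift of 4-6 SNOT-22 points between patients with and without polyps.

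**1. The plan's own figure.** n = 2 × 8² × 7.8 / 5² = 39.9, so 40 per group. Then 40 / 0.9 = 44.4, so 45 per group and 90 in total. The plan's figure reproduces (the unrounded multiplier 7.849 gives 41 instead of 40).

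**2. Arm sizes under simple randomisation.** The size of one arm is Binomial(90, 0.5).
- P(exactly 45/45) = 0.084.
- P(an arm below 40 before any dropout) = 2 × P(X ≤ 39) = 0.246.
- With 81 evaluable, P(both arms at least 40) = P(40) + P(41) = 0.176.
- With independent 10% dropout, both arms reach 40 in 20% of trials. A fixed 45/45 does so in only 50%, so much of the shortfall is not due to RAND.

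**3. Power cost of unequal arms.** Power = Φ(5/SE − 1.96), with SE = 8 × √(1/n₁ + 1/n₂).
- 40/40: SE = 1.789, power 79.8%.
- 35/45: SE = 1.803, power 79.2%.
- 30/50: SE = 1.848, power 77.2%.

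Averaged over Binomial(80, 0.5), power is 79.3%, a loss of 0.5 point.

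**4. Chance imbalance in polyp share.** The SD of the difference in share is about √(p(1−p) × 4/90), which is 0.084 at p = 0.2 and 0.105 at p = 0.5. Simulation (400,000 draws per prevalence) gives the probability that the arms differ by 15 points or more:

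| Assumed prevalence | Simple randomisation | Fixed 45/45, unstratified |
|---|---|---|
| 20% | 8.3% | 6.2% |
| 30% | 12.5% | 16.7% |
| 40% | 15.7% | 13.2% |
| 50% | 17.2% | 20.5% |
| 60% | 15.6% | 13.2% |

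The uneven second column reflects the coarse steps possible with 45 per arm. Fixing arm sizes alone does not address polyps.

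**5. What handling polyps is worth.** Take total variance 64, so the variance within polyp groups is s² = 64 − d² × p(1−p) for a shift d. With 90 patients, the variance of the treatment difference is:
- simple, unadjusted: the average of s²(1/n₁ + 1/n₂) + (d × difference in polyp share)²;
- simple, adjusted: the average of s² / Σ(n₁ₖn₂ₖ/nₖ) over the two polyp groups k;
- stratified and adjusted, with ideal balance: 4s²/90.

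The gain in sample size is the ratio of variances minus 1.

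| p, d | s² | SE simple, unadjusted | SE simple, adjusted | SE stratified, adjusted | Total gain | From adjustment | From allocation |
|---|---|---|---|---|---|---|---|
| 20%, 4 | 61.44 | 1.697 | 1.672 | 1.652 | 5.4% | 3.0% | 2.3% |
| 20%, 6 | 58.24 | 1.697 | 1.627 | 1.609 | 11.3% | 8.7% | 2.3% |
| 50%, 4 | 60.00 | 1.697 | 1.652 | 1.633 | 7.9% | 5.5% | 2.3% |
| 50%, 6 | 55.00 | 1.697 | 1.582 | 1.563 | 17.8% | 15.2% | 2.3% |

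These variances give 5-18%. Simulated standard errors with the same inputs scatter a little more widely, so roughly 3-19% is a fair range. Adjustment supplies the larger part in every row. The allocation change supplies about 2%, and 0-3% allowing for simulation scatter.

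**The case against.** The strongest reply is that simple randomisation is a valid method. It balances every factor in expectation, it cannot be predicted by an unblinded surgeon, and here it costs half a point of power. All of that stands. It rules out a reading that a reader might reach, namely that the trial is biased or materially underpowered because 45/45 is unlikely.

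Simple randomisation is also an inference. RAND can sort a fixed 45/45 list, which would fit the arm sizes in section 3d. The draw after consent in section 3b points the other way but does not settle it. A reader might further infer that, because RAND recalculates, no checkable record of allocation will exist. The documents do not support that: they are silent on storage, and drawn values can be saved.

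Polyposis should not be over-read either. Section 1a names it as one cause of failure, with failure defined in the cited meta-analysis as further surgery. It does not say that baseline polyps predict month-24 SNOT-22, and Aim 3 speaks of frontal sinus pathology without naming polyps. Baseline SNOT-22, which is also collected, is another reasonable covariate. What remains is that the plan names a plausible prognostic factor and uses it nowhere.

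Finally, a blocked list can make concealment worse. Only the subject is blinded (section 2c), a single faculty member is involved (section 9, item 11), and the physician or a team member obtains consent (section 8g). A list open to that team would be a step backwards, so a blocked list needs a separate holder.

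**Conclusion.** The point holds as a low-cost improvement. Allocation is under-described and most naturally reads as simple randomisation. The comparison remains unbiased, and missing 45/45 costs under 1 point of power. Chance imbalance of 15 points or more in polyp share would occur in about 8-17% of trials at 20-60% prevalence. Handling polyps is worth roughly 3-19% of sample size if they shift SNOT-22 by 4-6 points at 20-50% prevalence.

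A reader might credit that whole gain to stratified randomisation. The calculation does not support this, because most of the gain comes from the analysis model. The prevalence and the shift are both assumptions, since the documents give neither. With no shift, there would be essentially no gain from adjustment.

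**What to change.** In section 3d, state that the month-24 SNOT-22 difference and its confidence interval come from a model with treatment and polyp status (yes/no) recorded before surgery. This is one sentence, uses information close to what Aim 3 already requires, and brings most of the benefit.

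In sections 2c and 3b, replace the RAND sentence. Generate the list in advance in permuted blocks of mixed, undisclosed size within polyps yes/no. Save it as fixed, dated values, have it held by someone who neither recruits nor operates, and reveal one assignment at a time after consent. If RAND was always meant to order a fixed list, say so and add the same concealment step.

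The cost is a few sentences, about an hour to build the list, and a named holder. The downside is slight predictability at the end of a block for an unblinded surgeon, which concealment and undisclosed mixed block sizes limit.

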### 3. Study Procedures

- a) **N** Is this project a multicenter study (i.e., same project is conducted elsewhere by a different investigator) OR does this study involve conduct of research at multiple sites? Is SLU acting as a coordinating center for other sites OR is the SLU PI a direct recipient of a federal grant for this research? If yes, complete and attach the Supplemental Application for Coordinating Center Activities. Will the SLU site be participating in all parts/procedures/arms of the study?

**If No, explain what SLU will NOT participate in:**

**Protocol Title:** Randomized trial of Propel stent vs Kenalog-soaked Nasopore after Frontal Drill-out

---

**Please save frequently**

Page numbers from a sponsor's protocol/grant may be referenced in 3b, 3c, and 3d.

- b) **Describe all the procedures, from screening through end-of-study, that the human subject must undergo in the research project, including study visits, drug treatments, randomization and the procedures that are part of standard of care. Specify which procedures are for research and which are standard of care. Please note: The box below is for text only. If you would like to add tables, charts, etc., attach those files in the Attachment section (#16).**

Patients who present with chronic inflammatory frontal sinus pathology with indication for frontal sinus surgery will be evaluated for frontal drill out candidacy per physician judgment and consented. Once consented, the patients will be randomized 1:1 using the "rand" function (random number generator) in Microsoft Excel program. Nasopore group will receive frontal drill out procedure as indicated with Kenalog-soaked Nasopore while the Propel stent group will receive the Propel Stent after frontal drillout. Lund-McKay CT staging system, a part of the standard of care, to determine overall and frontal sinus score will be used to help stage and evaluate patients pre-operatively. A preoperative SNOT-22 score, also done as standard of care, will be obtained to assess symptom burden. Those who undergo the procedure and have consented to participate in the study will be asked to present to the otolaryngology clinic for regularly scheduled follow-up as part of standard of care, where symptoms and complications will be assessed. Rigid nasal endoscopy and SNOT-22 score are standard of care for routine follow-up of patients with chronic inflammatory sinonasal disease and will be performed at each of the 5 visits: post-operatively 1-2 weeks, 6-8 weeks, month 6, month 12, and month 24. This data will be abstracted from the records for research purposes. The data collected from the medical record includes the patient's current ENT-related active medical problems.

Note that to maintain uniformity in care, post-operative antibiotics (defined as up to day 60 post-op) will only be given to patients in any group if frank purulence is noted intra-operatively. In addition, in accordance with other trials involving drug eluting stents [1], oral and topic steroids will not be given to patients in any group until 60 days post-operatively. Because oral steroids and certain antibiotics have anti-inflammatory properties, this could confound the result of the study. For this reason, we wish to avoid using them in a random fashion.

- c) **If the proposed study is a clinical trial where a drug, vaccine, device or other treatment is compared to a placebo group or comparison treatment group, what are the guidelines or endpoints by which early decisions regarding efficacy or lack of efficacy can be made? For example, it may be reasonable to stop enrollment on a study when efficacy has already been clearly demonstrated, to avoid unnecessary enrollments of additional subjects. Alternatively, it may be reasonable to stop enrollment when it is clear that efficacy will never be demonstrated, given the statistical power of the study as designed. Describe the guidelines that are in place to assist in making these determinations, if relevant to the proposed study.**

A difference in mean post-operative SNOT-22 score of 9 points will be considered a clinically significant difference. [1]

As such, preliminary analyses will be performed once 5 patients have been enrolled and then every 6 months thereafter until 2 years of follow up of the last subject. If clear statistically significant inferiority or superiority is demonstrated, the trial will be stopped.

[1] Chowdhury NI, Mace JC, Bodner TE, et al. Investigating the minimal clinically important

**Protocol Title:** Randomized trial of Propel stent vs Kenalog-soaked Nasopore after Frontal Drill-out

difference for SNOT-22 symptom domains in surgically managed chronic rhinosinusitis. Int Forum Allergy Rhinol. 2017;7(12):1149-1155.

- d) **Describe how data analysis will be performed (statistical tests, methods of evaluating data) and indicate the smallest group/unit for which separate reporting will occur. For studies involving a questionnaire, if data and reliability information are available, please describe or provide references. For full board, unfunded studies describe sample size determination and power analysis. If none, please justify.**

The SNOT-22 score assesses symptomatic improvement and burden for patients with rhinosinusitis and is a clinically validated measure with high internal validity, correlation to its impact on quality of life, and longitudinal stability after sinus surgery. The minimal clinically important difference (MCID) for SNOT-22 is 9 points. [1, 2, 3, 4,5] From historical SLU otolaryngology practice data, patients who present to the otolaryngology clinic undergoing sinonasal surgery have a mean SNOT-22 score of  $42.0 \pm 8.0$ .

For this randomized, active control study of two types of sinonasal stents with steroid, we are interested in determining whether the cheaper and more available alternative (Nasopore and Kenalog) is similar to an accepted treatment (Propel stent) in symptom control at 24 months as measured by post-operative SNOT-22 scores.

For our sample size determination, we explore the lower limit of a 95% confidence interval (CI) around the mean difference between post-operative SNOT-22 scores of the two groups. We'll define the lower limit of the CI, or the margin of inferiority, as -8, which does not include the predetermined MCID of -9.  
We set power = 0.8 and alpha = 0.05.

Given: # subjects in each group =  $n = [(2(SD)^2) * (z_{1-(\alpha/2)} + z_{1-B})^2] / [(u_1 - u_2)^2]$  [ref 6]  
SD = 8.0, from SLU historical data  
 $[(z_{1-(\alpha/2)} + z_{1-B})]^2 = 7.8$ , estimated from z-tables,  $\alpha = 0.05$  and  $B = 0.2$

IF  $u_1 - u_2 = -8$  then  $n = 16$  subjects

To be conservative in our sample size calculation, we'll use  $u_1 - u_2 = -5$ , which yields a sample size of 40.

If we assume attrition rate of 10%, we estimate we'll need 45 subjects per group and a total of 90 subjects.

Difference in rates of complications will also be determined by chi-square testing for equality of proportions between groups. As these outcomes are expected to be few, our target sample size may not be adequate to determine statistical significance of differences. Reporting these complication rates nonetheless informs clinical practice.

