**h) Inclusion and Exclusion Criteria.**

**Identify inclusion criteria.**

Adults  $\geq 18$  and  $\leq 90$  years of age  
Patients able to speak and understand English.  
Patients for whom frontal drill out procedure is medically indicated as judged by attending physician surgeon.

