- b) The data will be monitored by [name] (MD, Assistant Professor of SLU Department of Otolaryngology), who is the PI of the study.
- c) The aggregate data will be formally reviewed once every 10 patients have completed follow up.
- d) [name] will be reviewing SAEs in real time as he is the only faculty (at SLU or otherwise) who will be involved in the study. We don't expect the AE frequency, type and severity to be significantly different between the Kenalog and Nasopore groups as the treatment options are quite similar. This is because the surgical technique (i.e. the frontal drill-out) is identical - the only difference is the type of stent (both of which have steroids), and the AE profile of both interventions is similar and treatable (see section 9, subpoint 4). Regardless, we are planning to record and review the AE number and type (major, minor) every after the first 5 patients have enrolled and then every then every 6 months thereafter until 2 years of follow up of the last subject.
- e) n/a

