#### \*\*\* Informed Consent \*\*\*

#### 13. Informed Consent

Federal regulations require that informed consent be obtained from individuals prior to their participation in research unless the IRB grants a waiver of consent. Answer the questions, below, then click Add to provide the necessary consent documents and information regarding subject consent. Multiple consents/waivers may be added, but they must be uploaded one at a time.

**NOTE:** You may refer to the SLU IRB Guidance for Obtaining Informed Consent for considerations regarding the consent/assent process.

State N/A if not applicable.

- 1) How is consent being obtained? When and where will the discussion take place? If the study involves a Non-English Speaking participant/population, please include details about plans for translated

**Protocol Title:** Randomized trial of Propel stent vs Kenalog-soaked Nasopore after Frontal Drill-out

consent materials and interpreters to be used (see SLU Guidelines for Involving Non-English Speaking Subjects for more details).

Patients who present in clinic with chronic inflammatory frontal sinus pathology with indication for frontal sinus surgery will be evaluated for frontal drill out candidacy per physician judgment and consented. Informed consent will be sought from the patient at this out-patient visit prior to their procedure. The patients will have no limit on time to consent. The PI or study team member will initially discuss the study with the potential subject, including the risks, benefits, and alternatives. The subject will be provided with information about the study and their role. They will be informed that they may terminate their participation at any time for any reason. If they agree to participate, consent will be signed at that time.

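### The plan states neither allocation concealment nor when the surgeon learns the arm; disclosing it only after the drill-out would keep it out of every earlier decision

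*Combined protocol and SAP*

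**What the plan says.** - **Allocation.** Section 3b: "Once consented, the patients will be randomized 1:1 using the" Excel random-number function. Section 2c says the same in fewer words. Neither says who makes the draw, who holds it, whether it is logged or can be repeated, or when it is disclosed.
- **Blinding.** Section 2c: "Single blind (Subject) randomized, active control study". The surgeon is not blinded.
- **Consent.** Section 13, item 1: "Informed consent will be sought from the patient at this out-patient visit prior to their procedure".
- **Eligibility.** Section 8h includes "Patients for whom frontal drill out procedure is medically indicated as judged by attending physician surgeon". Section 3b places this judgment before randomization.
- **Where the arms part.** Section 3b: "Propel stent group will receive the Propel Stent after frontal drillout". In section 2c, too, the product goes in at the end of the operation. The Data Safety Monitoring Plan (section 9, item 11b) says that "the surgical technique (i.e. the frontal drill-out) is identical - the only difference is the type of stent".
- **Staffing.** The same plan says of the PI that "he is the only faculty (at SLU or otherwise) who will be involved in the study".
- **Follow-up.** Section 3b: "Those who undergo the procedure and have consented to participate in the study will be asked to present to the otolaryngology clinic". Section 8k likewise describes follow-up after the procedure. Section 3d names no analysis population.
- **Intra-operative finding.** Section 3b makes post-operative antibiotics depend on purulence seen during surgery, and notes that some antibiotics could confound the result.

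**The concern.** The wording in 3b fixes an order (consent, then draw) but no date and no custodian. A draw in the operating room is compatible with it. So is a draw in clinic whose result the surgeon knows well before the operation.

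Under the second reading, several judgments fall after the arm is known: whether the patient is still a candidate, whether surgery is cancelled, how the drill-out is carried out, and whether purulence is recorded. One faculty member is involved, and section 10b says a patient outside the study still receives one of the same two products at a named individual's choice. Follow-up is described only for patients who undergo the procedure, so a patient randomized and then not operated on could drop out of the comparison.

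The groups compared at 24 months could then differ from the groups randomized. Blinding the subject does not protect against this. The bias can go either way; in Nasopore's favour, it makes a false non-inferiority claim more likely.

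**Working it through.** **1. The plan's own figures (section 3d).** With n = 2 x SD² x 7.8 / difference² and SD 8:
- difference 8: 2 x 64 x 7.8 / 64 = 15.6, so 16;
- difference 5: 2 x 64 x 7.8 / 25 = 39.9, so 40;
- 10% attrition: 40 / 0.9 = 44.4, so 45 per group and 90 in total.

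All reproduce. The point below does not change them.

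**2. Inputs for the illustration.** From 3d: SD 8, margin 8 points, 45 per arm, two-sided 95% interval (2.5% one-sided). Assumed, because the documents give neither: k = 2 or 4 worst-outlook patients of 45 lost from one arm between allocation and surgery, and a correlation rho of 0.3 or 0.5 between pre-operative outlook and the 24-month score. The only loss figure in the plan is the overall 10% attrition (45 x 0.10 = 4.5 per arm). It says nothing about timing or arm.

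**3. Shift in the arm mean.** Shift = 8 x rho x m, where m is the size of the mean of the 45 - k remaining standard normal values after the worst k are removed: about 0.093 for k = 2 and 0.171 for k = 4. Example: 8 x 0.5 x 0.171 = 0.68 points.

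**4. False non-inferiority when Nasopore is truly worse by exactly 8 points.** The approximation is Phi(-1.96 + shift / SE), with SE = 8 x sqrt(1/(45 - k) + 1/45). For k = 4, SE = 1.73 and -1.96 + 0.68/1.73 = -1.57, which gives about 5.9%. Simulation (60,000 trials, pooled t interval; 2.5% with no loss) gives:

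| k | rho | Shift (points) | Loss from Nasopore only | Loss from Propel only | Equal loss |
|---|---|---|---|---|---|
| 2 | 0.3 | 0.22 | 3.4% | 1.8% | 2.5% |
| 2 | 0.5 | 0.37 | 4.1% | 1.6% | 2.7% |
| 4 | 0.3 | 0.41 | 4.4% | 1.4% | 2.6% |
| 4 | 0.5 | 0.68 | 6.0% | 1.0% | 2.8% |

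**5. Arm-aware surgery.** SE = 8 x sqrt(2/45) = 1.69. An assumed average effect of 0.5 point gives 4.8% if it favours Nasopore and 1.2% if it favours Propel. The documents offer no source for 0.5.

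**6. What late disclosure cannot reach.** Suppose k Nasopore patients receive Propel after disclosure, and non-inferiority is claimed only if the as-assigned and per-protocol analyses agree. If the k patients are random, the error is 2.5% for k = 2 and for k = 4. If they are the worst-outlook patients, it is 3.2%, 3.8%, 4.0% and 5.3%, in the row order of the table.

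**The case against.** **The wording may already protect enrolment.** The natural reading of 3b is a draw per patient after candidacy and consent, with no list to foresee. That stands. A reader might infer that allocation is unconcealed, or that selection took place. The documents are silent on concealment, which shows neither. An advance list is not needed either, provided each patient has one logged draw.

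**Late disclosure may look like a complete cure.** A reader might infer that it closes all surgeon-driven selection, or that requiring both analyses to agree restores 2.5%. Neither is supported. The surgeon is unblinded once the product is named, the patient may leave at any time (section 8g), and step 6 shows that selective crossover still leaves about 3-5%.

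**The illustration is thin.** It needs losses concentrated in one arm and among the worst patients. Equal loss barely moves the error, and loss from Propel makes the test conservative. That is fair, and it is why the figures show sensitivity and do not estimate bias.

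**The cost may be more than trivial.** Section 3d describes Nasopore with Kenalog as the cheaper and more available option, the funding checklist says none, and section 7 sets hospital pharmacy requirements for study drugs. Against this, 3f says both devices are in routine use, and sections 8g and 13 mention study team members besides the physician. The burden looks small, but that is a judgment, since the documents do not price it.

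**Conclusion.** The point holds as a gap with a better method available. Concealment and the time of disclosure are unspecified, and the plan permits the sole faculty investigator to know the arm before and during a drill-out that does not depend on it. Disclosure after the drill-out would keep the arm out of cancellation, exclusion, conduct of the surgery and the purulence finding. It would not stop selective crossover or withdrawal afterwards, and it would not blind post-operative care.

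Under the assumed loss of 2 to 4 worst-outlook Nasopore patients of 45 and a correlation of 0.3 to 0.5, false non-inferiority rises from 2.5% to about 3.4-6.0%. The same loss from Propel lowers it to about 1.0-1.8%. The actual size cannot be computed from the documents. No stated figure in the plan is wrong on this account. The change should be made; confidence is medium.

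**What to change.** Replace the randomization text in 2c and 3b with:

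> Consent is obtained in clinic. A study team member who is not operating makes a single logged 1:1 draw per patient (Excel rand may be used), keeps it from the surgeon and recruiting staff, and discloses it only once the drill-out is complete.

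Add to 3d:

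> All randomized patients are followed and analysed in the assigned group, with a per-protocol analysis reported alongside. Patients consented but not allocated are counted with reasons.

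Two details make this enforceable. The log should sit apart from the study data, which section 11c opens to all study team members. The time of the draw should also be stated: if it is made at the end of the drill-out, a patient who leaves earlier has no arm; if earlier, that patient counts as randomized. Crossovers and withdrawals after disclosure should be reported by arm with reasons, because the timing rule cannot prevent them.

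**Cost.** Sample size, visits and measurements do not change. Both products must be on hand for each case, and an existing non-operating team member must be available to disclose the assignment.
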